5.1.3 End-of-Study

All patients should return to the clinic for end-of-study assessments 28 (± 7) days after the last dose of lucitanib has been administered.

The trial will be completed when all enrolled patients have discontinued treatment and completed the end-of-study follow-up visit.

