9.3 End-of-Study Visit (all patients)

The following procedures will be performed for all patients 28 days (± 7 days) after the last dose of protocol-specified treatment:

- Complete physical examination
- Weight
- ECOG performance status
- Vital signs (BP, pulse, and temperature)
- Concomitant medications since last visit
- Contraceptive counseling
- Serum pregnancy test for women of childbearing potential
- Hematology (including reticulocyte count), and serum chemistry
- Urinalysis
- Tumor scans (using the same methodology as was used at screening), including brain scans for patients with brain lesions at baseline, unless it has been < 2 weeks since last scan or disease progression was noted on the last scan
- Blood sampling for ctDNA analysis
- Blood sampling for biomarker analysis
- AE monitoring (until 28 days after last dose of protocol-specified treatment; all ongoing SAEs should be followed until resolution or stabilization. After the 28-day window, only new SAEs assessed as related to study drug should be recorded)
- Review and collection of BP and dosing diary
- 12-lead ECG (in triplicate, 10-sec tracings > 2 min apart)

- LVEF (ECHO or MUGA)
- QoL questionnaire (FACT-B)
- Survival status
- Subsequent therapies for breast cancer
- Optional post-treatment biopsy for PD analyses, at time of disease progression and before subsequent anti-line therapy is initiated

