12 PATIENT DISPOSITION

12.1 Patient Discontinuations

A patient must be discontinued from protocol-prescribed therapy if any of the following apply:

- Consent withdrawal at the patient's own request or at the request of their legally authorized representative
- Progression of patient's underlying disease, unless in the opinion of the investigator and approved by the sponsor, the patient has indolent progression with evidence of continued clinical benefit from treatment. This must be approved by the sponsor and reviewed on a case by case basis
- Any event, adverse or otherwise, that, in the opinion of the investigator, would pose an unacceptable safety risk to the patient
- An intercurrent illness that, in the opinion of the investigator, would affect assessments of the clinical status to a significant degree and requires discontinuation of therapy
- A positive pregnancy test at any time during the study
- Major non-compliance that may affect patient safety
- Investigator decision

In addition, the sponsor may discontinue the trial early for any of the reasons noted in [Section 13.6](#).

The sponsor (or designee) should be notified of all study terminations as soon as possible. The date and reason for cessation of lucitanib must be documented in the eCRF and source documents.

To the extent possible, end-of-study procedures should be performed on all patients who receive lucitanib. The end-of-study visit should occur 28 ± 7 days following the last dose of lucitanib. After stopping protocol-specified treatment, all patients will remain in the study and will be followed for safety (through 28 days after last dose; those with ongoing SAEs will be followed until either resolution or stabilization has been determined), and for survival status by telephone (at approximately two monthly intervals, until death).

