## **15 PATIENT REPORTED OUTCOMES**

PROs will be measured using the FACT-B questionnaire in all patients with both a baseline assessment and at least one post-baseline assessment.

The baseline PRO measurement will be defined as the last value prior to or on the day of the first dose of lucitanib. The on-treatment period will be defined as the day after the first dose of lucitanib to 28 days after the last dose of protocol-specified treatment. PRO measurements collected during the on-treatment period will be included in the summary tables.

The summary of PRO data will include descriptive statistics (N, mean, standard deviation, median, minimum, and maximum) of the maximum, minimum, and last value during the on-treatment period. Summaries using descriptive statistics of the change from baseline to the maximum, minimum, and last value during the on-treatment period will also be given by relevant cohort.

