### **17.2** Clinical Laboratory Evaluations

Clinical laboratory evaluations include variables for hematology, serum chemistry, and urinalysis. Laboratory values will be presented in Systeme International (SI) units. The baseline laboratory value will be defined as the last value prior to or on the day of the first dose of oral lucitanib. The on-treatment period will be defined as the day after the first dose of oral lucitanib to 28 days after the last dose of lucitanib. Laboratory values collected during the on-treatment period will be included in the summary tables. The laboratory values collected after the on-treatment period will only be presented in the data listings.

The summary of laboratory data will include descriptive statistics (N, mean, standard deviation, minimum, median, and maximum) of the maximum, minimum, and last value during the treatment period by treatment group. Summaries using descriptive statistics of the change from baseline to the maximum, minimum, and last value during the on-treatment period will also be presented by treatment group.

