## 17.3 Vital Signs

The baseline vital sign measurement will be defined as the last value prior to or on the day of the first dose of lucitanib. The on-treatment period will be defined as the day after the first dose of lucitanib to 28 days after the last dose of protocol-specified treatment. Vital sign measurements collected during the on-treatment period will be included in the summary tables. The vital sign measurements collected after the on-treatment period will only be presented in the data listings.

The summary of vital sign data will include descriptive statistics (N, mean, standard deviation, minimum, median, and maximum) of the maximum, minimum, and last value during the on-treatment period by treatment group and study phase. Summaries using descriptive statistics of the change from baseline to the maximum, minimum, and last value during the on-treatment period will also be presented by treatment group. Shift tables and graphical representations of vital signs parameters may be provided.

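### FACT-B is tabulated only to day 28 after last dose, but the End-of-Study visit that collects it may fall on days 21 to 35, so some on-schedule questionnaires are left out by appointment date

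*SAP*

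**What the plan says.** **Analysis window.** SAP section 15 starts the on-treatment period the day after first dose and runs it "to 28 days after the last dose of protocol-specified treatment". It then states that "PRO measurements collected during the on-treatment period will be included in the summary tables". The summaries are the maximum, minimum and last on-treatment value, and the changes from baseline to each. Protocol section 11.2.6 has the same window. The patients analysed are those with a baseline and at least one post-baseline assessment; that condition does not mention the on-treatment period.

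**Visit window.** Protocol section 12.1 states: "The end-of-study visit should occur 28 ± 7 days following the last dose of lucitanib". Protocol sections 5.1.3 and 9.3 and SAP section 2.2.3 give the same tolerance. Section 9.3 lists FACT-B, laboratory tests and vital signs among the procedures at this visit.

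**FACT-B schedule.** Protocol section 9.5.8 places the questionnaire on Day 1 of Cycles 1, 3, 5 and 7, then every third cycle from Cycle 10, and at End-of-Study.

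**Laboratory values and vital signs.** SAP sections 17.2 and 17.3 use the same 28-day limit but say what happens to later values: "The laboratory values collected after the on-treatment period will only be presented in the data listings", and "The vital sign measurements collected after the on-treatment period will only be presented in the data listings". SAP section 15 has no such sentence for FACT-B.

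**The concern.** The two windows do not match. Two patients who both comply with the visit schedule, one seen on day 28 and one on day 29, are treated differently in the FACT-B tables, and only the appointment date separates them.

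Two groups are affected.

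- **Early stoppers.** The first on-treatment questionnaire after baseline is at Cycle 3 Day 1. For a patient who stops before then, End-of-Study is the only scheduled post-baseline FACT-B. If it is completed on days 29 to 35, the patient meets the condition for the PRO analysis but has no value to tabulate.
- **Later stoppers.** If the End-of-Study value is excluded, the last value becomes the previous scheduled questionnaire. The schedule has gaps of two cycles up to Cycle 7 and three cycles after it, so that questionnaire may date from up to about 8 or 12 weeks before stopping.

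SAP section 16.1 allows no imputation, so nothing takes the place of the excluded value. The same section calls for the fullest possible use of the data, which sits awkwardly with leaving out a planned, on-schedule assessment.

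**Working it through.** The documents state no figure for values lost, so there is no plan figure to reproduce. The check has three steps.

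**1. Count of visit days**

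- Permitted visit days: 28 − 7 = 21 to 28 + 7 = 35, which is 15 days.
- Days after the cut-off: 29 to 35, which is 7 days. Day 28 itself is inside the analysis window.
- Share of permitted days outside the tables: 7/15 = 46.7%.

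**2. Share of visits after day 28**

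This depends on visit timing, which the documents do not give. Every row is an assumption.

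| Assumed timing of visits within days 21–35 | Share after day 28 |
|---|---|
| Uniform over the 15 days | 46.7% |
| Triangular, centred on day 28 | 43.8% |
| Normal (by whole day), centred on day 28, SD 1 / 2 / 3 / 4 days | 30% / 40% / 43% / 45% |
| Half exactly on day 28, the rest evenly early or late | 25% |
| Three quarters exactly on day 28, the rest evenly early or late | 12.5% |
| Centred on day 26, SD 2 | 10% |
| Centred on day 30, SD 2 | 78% |

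The logical limits are 0% and 100%. Symmetric timing with no more than half of visits exactly on day 28 gives about 25% to 47%.

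**3. Patients who lose their only tabulated post-baseline FACT-B**

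Inputs:

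- Cycle 3 Day 1 is study day 2 × 28 + 1 = 57, so the relevant stoppers are those who stop within the first 8 weeks, or 8/4.348 = 1.84 months.
- Time on drug is not given. I assume it is exponential and bracket the median with two PFS figures from the protocol used as stand-ins: 4 months (the threshold in section 11.3) and 9.4 months (the earlier breast cancer result in section 3.6.1.2, read here as a median).

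Formula: P(stop before week 8) = 1 − 2^(−1.84/median).

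- Median 4 months: 1 − 2^(−0.460) = 27.3%.
- Median 9.4 months: 1 − 2^(−0.196) = 12.7%.

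Multiplying by the late-visit share:

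| Median time on drug | 25% late | 46.7% late |
|---|---|---|
| 4 months | 0.273 × 0.25 = 6.8% | 0.273 × 0.467 = 12.7% |
| 9.4 months | 0.127 × 0.25 = 3.2% | 0.127 × 0.467 = 5.9% |

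The range is roughly 3% to 13%. Off-centre timing widens it, from 0.127 × 0.10 = 1.3% to 0.273 × 0.78 = 21%. All these figures assume that every early stopper attends End-of-Study and completes FACT-B; deaths, withdrawals and missed visits would lower them.

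**After the change.** With a limit of last dose + 35 days, 0 of the 15 permitted days fall outside the tables.

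**The case against.** **The size is assumed.** The visit target is day 28, which is inside the analysis window. Protocol section 9.5.1.4 also asks for the End-of-Study ECG no later than 28 days after last dose, and adverse event collection ends at day 28, so sites may tend to book early. The 4-month figure is a decision threshold for PFS and says nothing direct about time on drug. Protocol section 12.1 asks for End-of-Study procedures only as far as possible. All of this stands. It is why the sizes above are ranges, but it does not remove the mismatch, because days 29 to 35 remain on schedule for the visit.

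**Early stoppers are not removed from the PRO population.** A reader might infer that they are, and that the FACT-B results are therefore biased upward. The documents do not support this. A patient with a day-32 questionnaire still meets the stated population condition. Exclusion turns on appointment date, early stoppers seen by day 28 stay in the tables, and patients may stop for toxicity as well as progression. The direction of any bias is open.

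**The laboratory and vital-sign window is defensible.** A reader might also infer that about half of all End-of-Study laboratory and vital-sign values are lost. They are not lost: late values stay in the data listings. The 28-day limit matches the adverse event period in SAP section 17.1. With a half-life of 31 to 40 hours (protocol section 3.6.1.1), day 28 (672 hours) is already 672/40 = 17 to 672/31 = 22 half-lives after last dose. Moving laboratory values to day 35 while adverse events stay at day 28 would create a new inconsistency. This objection stands, and the point is therefore confined to FACT-B.

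**Conclusion.** The mismatch is on the page and needs no assumption: 7 of the 15 permitted End-of-Study days lie outside the FACT-B tables, with no visit-windowing rule and no exception. For a patient who stops before Cycle 3 Day 1, the excluded value can be the only post-baseline one; for others, the last value is moved back to an earlier questionnaire.

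How many patients this touches cannot be read from the documents. The 3% to 13% range rests on exponential time on drug with a median of 4 to 9.4 months, 25% to 47% of visits falling after day 28, and full attendance and completion at End-of-Study.

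The severity is minor. Only descriptive summaries of a secondary endpoint are affected; the primary endpoint and the sample size are untouched. It is a cheap improvement worth making before database lock.

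**What to change.** In SAP section 15, include the nominal End-of-Study FACT-B in the summaries whatever its day within the 28 ± 7 day visit window; equivalently, end the PRO window at last dose + 35 days. Record this as a departure from protocol section 11.2.6, which carries the 28-day limit. State in the same place how a questionnaire completed after day 35 is handled, since section 15 currently has no rule for values outside the window.

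Leave the laboratory and vital-sign windows (SAP sections 17.2 and 17.3) and the 28-day adverse event rule (SAP section 17.1) as they are.

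The cost is one sentence in the SAP and a note of the departure, with no new data or visits. The downside is that a few values up to 7 days further off drug, some possibly after the next therapy has begun, enter the PRO summaries. If that is a worry, reporting End-of-Study FACT-B as a separate off-treatment row would also show the values.

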4.2.2 Secondary Endpoints

- ORR according to RECIST Version 1.1
- DR and DCR according to RECIST Version 1.1
- OS
- Change from baseline in PRO using the Functional Assessment of Cancer Therapy-Breast (FACT-B) questionnaire
- Treatment emergent AEs, laboratory abnormalities, physical examinations including vital signs and electrocardiogram (ECG) abnormalities
- PK parameters including area under the concentration (AUC) curve from time zero to time t (AUC_{0-t}), C_{max} , T_{max} , $t_{1/2}$, volume of distribution at steady state (V_{SS}/F), and total plasma clearance (Cl/F) for lucitanib, if data allow

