9.5.8 Quality-of-Life Assessments

QoL will be measured using the FACT-B questionnaire ([Appendix D](#)), which will be administered on Day 1 of Cycles 1, 3, 5, and 7. After Cycle 7, questionnaires will be collected every 3 cycles (on Day 1 Cycles 10, 13, 16, etc.), and at End-of-Study.

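### FACT-B is summarised only at each patient's maximum, minimum and last value, with no by-visit change; with two or more forms, change to the maximum or minimum is biased even when nothing has changed

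*SAP*

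**What the plan says.** Protocol 4.2.2 lists the secondary endpoint as "Change from baseline in PRO using the Functional Assessment of Cancer Therapy-Breast (FACT-B) questionnaire". It names no time point and no summary measure.

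SAP 15 gives descriptive statistics "of the maximum, minimum, and last value during the on-treatment period". It then adds that summaries of "change from baseline to the maximum, minimum, and last value during the on-treatment period will also be given by relevant cohort". Protocol 11.2.6 has the same plan, in the same terms: "change from baseline to the maximum, minimum, and last value". The analysis set needs a baseline form and at least one later form, so one post-baseline form is enough.

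The on-treatment period runs from "the day after the first dose of lucitanib to 28 days after the last dose of protocol-specified treatment".

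Collection is at fixed visits. Protocol 9.5.8 has the questionnaire "administered on Day 1 of Cycles 1, 3, 5, and 7", and then: "After Cycle 7, questionnaires will be collected every 3 cycles". There is also a form at End-of-Study, which Protocol 5.1.3 and 9.3 place 28 ± 7 days after the last dose.

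Nothing elsewhere fills the gap. SAP 4 adds only generic descriptive statistics, SAP 11.2 repeats the endpoint, SAP 14 covers the exploratory endpoints, and SAP 16.1 rules out imputation. Where the SAP wants a summary by time point it says so, as for ECGs in SAP 17.4.

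**The concern.** The largest of several noisy scores tends to lie above the patient's true level and the smallest below it. The gap widens with the number of scores. Patients who stay on treatment longer complete more forms, so their maximum looks better and their minimum looks worse for that reason alone. One table could then show average improvement and average deterioration together in patients whose quality of life did not move.

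This also affects comparisons between groups. SAP 4 presents summaries by initial dose (10 mg, 15 mg), while SAP 15 gives FACT-B change by cohort. Protocol 3.7 reports that 15 mg was hard for many patients to sustain. If time on treatment differs between the groups shown, their maxima and minima will differ even with identical quality of life. The documents do not say whether it will differ.

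The same three extracts are used for laboratory values and vital signs (SAP 17.2, 17.3), where an extreme is itself a safety signal. For an endpoint meant to estimate change in quality of life, they leave out the plainest summary, which is change at each planned visit.

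**Working it through.** The plan states no FACT-B sample size, SD or effect, so there is no figure of its own to reproduce. The check asks what the planned summary returns when the truth is no change.

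**Inputs**
- Post-baseline forms at Day 1 of Cycles 3, 5, 7, 10, 13, 16 and so on. With 28-day cycles these fall 56, 112, 168, 252, 336 and 420 days after Cycle 1 Day 1, plus End-of-Study (Protocol 9.5.8).
- Errors at different visits independent and normal, with single-visit within-patient SD σ (assumption). Stable differences between patients cancel in change from baseline.
- Time on treatment exponential (assumption), with median 2, 4, 6 or 9.4 months. Four months is the PFS threshold in SAP 3 and 9.4 months is the PFS in Protocol 3.6.1.2. Both serve only as stand-ins, because treatment duration is not given.

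**Step 1: bias for k forms.** With no true change, the expected change from baseline to the maximum is σ·e(k), where e(k) = ∫ x·k·φ(x)·Φ(x)^(k−1) dx. The change to the minimum is −σ·e(k).

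| k | 1 | 2 | 3 | 4 | 5 | 6 | 7 | 8 |
|---|---|---|---|---|---|---|---|---|
| e(k) | 0 | 0.564 | 0.846 | 1.029 | 1.163 | 1.267 | 1.352 | 1.424 |

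Change at any fixed visit has expectation 0 under the same truth, and so does change to the last value.

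**Step 2: average over the schedule.** Suppose every patient also has an End-of-Study form in the window. Then k is 1 plus the number of scheduled visits reached, and the mean bias is Σ P(T ≥ t_j)·[e(j+1) − e(j)]. With a 4-month median (121.75 days), P(T ≥ t) = 2^(−t/121.75):

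- 56 days: 0.727 × 0.564 = 0.410
- 112 days: 0.529 × 0.282 = 0.149
- 168 days: 0.384 × 0.183 = 0.070
- 252 days: 0.238 × 0.134 = 0.032
- 336 days: 0.148 × 0.104 = 0.015
- 420 days: 0.092 × 0.085 = 0.008
- 504 days: 0.057 × 0.072 = 0.004

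These sum to about 0.69. A simulation of 400,000 patients gives 0.694 with all later visits included.

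| Assumed median time on treatment | Mean forms | Mean bias with End-of-Study form | Mean bias without it |
|---|---|---|---|
| 2 months | 2.0 | 0.41 σ | 0.40 σ |
| 4 months | 3.3 | 0.69 σ | 0.67 σ |
| 6 months | 4.4 | 0.87 σ | 0.84 σ |
| 9.4 months | 6.3 | 1.06 σ | 1.03 σ |

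Mean forms are for the case with the End-of-Study form. Without it, only 53% (2 months) to 87% (9.4 months) of patients have any post-baseline form, and the last column is for them.

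**Step 3: sensitivity.**
- If σ were 5, 7.5 or 10 points (assumed; the documents give no SD), the 4-month case is 3.5, 5.2 or 6.9 points in each direction.
- If visit errors share a constant correlation ρ, e(k) is multiplied by √(1 − ρ). The bias shrinks and vanishes only at ρ = 1.
- σ is the SD of one visit's error. In units of the SD of a difference between two visits, divide by √2: 0.564 becomes 0.40 and 1.029 becomes 0.73.

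**Step 4: the last value.** The End-of-Study visit may fall 21 to 35 days after the last dose, but the window closes at day 28. Of those 15 possible days, 21 to 28 (8 days) are inside and 29 to 35 (7 days) are outside. A patient seen on day 27 has an off-drug form as the last value. One seen on day 30 has the last scheduled form instead, and after Cycle 7 scheduled forms are 3 × 28 = 84 days apart.

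**The case against.** The best defence is that FACT-B is a descriptive secondary endpoint in an open-label phase 2 study. The decision rules in SAP 3 use PFS only, and no test or threshold rests on FACT-B. SAP 15 says what the summary will include, which does not forbid by-visit tables, and the data for them will exist. Change to the last value is a change from baseline and is not biased by taking an extreme. With real change, the extremes carry signal as well as noise. By-visit means are affected by dropout too.

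Most of this stands, and it limits the point without removing it. Wording that permits a by-visit table does not commit to one. The last value is the only unbiased extract of the three, and it answers a question at no defined time.

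A reader might infer more than the documents support:
- **That all three extracts show false gains or losses.** The last value does not, nor does any extract for a patient with one post-baseline form, where the three coincide.
- **That the secondary objective cannot be answered.** The objective is to estimate patient-reported outcomes after treatment, with no time point fixed. Change to the last value answers it, weakly.
- **That 1.35 SD, the value for seven forms, is typical.** Seven forms require reaching Cycle 16 Day 1, day 420 or about 13.8 months, plus an End-of-Study form. The schedule averages are well below that.

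**Conclusion.** The point holds for the maximum and minimum, and for the missing by-visit summary. With two or more post-baseline forms, mean change to the maximum is biased upward and to the minimum downward with no true change, and more so the longer patients stay. The size is 0.56 single-visit within-patient SDs for 2 forms and 1.03 for 4, and about 0.4 to 0.9 SD over the schedule for assumed median treatment times of 2 to 6 months. It rests on independent normal errors and exponential treatment time; positive serial correlation reduces it. Whether it matters in FACT-B points depends on an SD that the documents do not give. The fault in the last value is mixed timing, not bias from extremes. It would be wrong to read every planned FACT-B figure as artefact. The primary endpoint is untouched, but the SAP should be changed because the better summary uses data already collected.

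**What to change.** In SAP 15, before database lock:

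- Make change from baseline at each scheduled visit (Day 1 of Cycles 3, 5, 7, 10 and so on) the main FACT-B summary, with forms expected, forms received and a 95% CI.
- Report End-of-Study separately, and include every form within that visit's 28 ± 7 day window rather than cutting off at day 28.
- Keep the maximum and minimum, if at all, as supplementary summaries, labelled as depending on the number of forms.
- Optionally add a repeated-measures model with visit and baseline score as support.

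The cost is SAP wording, one table and at most one standard model, with no new data. The downside should be stated in the SAP: by-visit means describe only patients still in the study at that visit, and the model assumes that missing forms are missing at random. Showing forms expected and received lets the reader judge the first; neither problem is removed.
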